## 6 STATISTICAL AND ANALYTICAL PLANS

The planned tables and listings are presented in Section 8.

### 6.1 Changes in the Planned Analyses

Any changes in the statistical analyses once the SAP has been finalised and the database has been locked should be documented at clinical study report (CSR).

### 6.2 Blind Review

A Blind Data Review Meeting (BDRM) is planned to occur before treatment unblinding takes place. The main objective of this meeting is to review data and identify protocol deviations in order to assign patients to all the analysis sets. Details of BDRM will be specified in a separate document.

A review of all major and critical protocol deviations and their potential consequences for the analysis will be conducted during the BDRM. Results and actions taken will be summarized in the Pre-Analysis Review document, which will be finalized before treatment unblinding.

A summary table will be provided including the number of patients with critical and major protocol deviations and the number of clinical and major protocol deviations. The protocol deviations will be listed. The number of patients per study population will be provided. Listings for patients excluded from the SAF, FAS and PP set will be provided.

## 6.3 Hypotheses and Statistical Methods

### 6.3.1 Definitions

Baseline	( Visit 1 (Day 1, 24 h after the cataract surgery).
Time calculation	Differences between dates to express duration will be calculated as the final date - initial date + 1. To convert these days differences to other units, the following conversion factors will be used: 1 year = 365.25 days and 1 month = 30.4375 days.  Ex. Age = (informed consent date – date of birth + 1) / 365.25
Absolute change from Baseline	Absolute change from Baseline at Visit X will be calculated as:  Absolute change from Baseline = Visit X - Baseline
Percentage change from Baseline	Percentage change from Baseline at Visit X will be calculated as:  Percentage change from Baseline [%] = ((Visit X - Baseline)/Baseline) *100  In case of Baseline = 0 no percentage change from baseline will be calculated.
Signs of ocular inflammation (yes/no)	The presence/absence of the different signs of ocular inflammation: Chemosis, Bulbar conjunctival injection, ciliary injection, corneal edema, keratic precipitates will be defined as:  No: grade=0 (absence)  Yes: grade=1, 2 or 3 (presence)
Conversion Snellen to LogMar	Step 1. Mar = Snellen Denominator/Snellen Numerator  Step 2. LogMar = log (Mar)  Example: Snellen 20/40  Mar = 40/20 = 2  LogMar= log(2) = 0.3
Treatment Emergent Adverse Event	Treatment Emergent Adverse Events (TEAEs) are defined as an event that emerges during treatment  having been absent pre-treatment or worsens relative to the pre-treatment state:  First dose IMP/Pacebo date ≤ start date AE ≤ last dose IMP/Placebo date
Rescue medication	The following prohibited medications will be considered as rescue medication when administered to subjects not responding to IMP or placebo: 

▪ Any systemic or local therapy with corticosteroids (other than the study drug) or immunosuppressant (except pre-surgical and/or surgical administration of 1 drop of a topical NSAID or corticosteroid, at the investigator discretion)

▪ Any topical ocular medication (except preservative-free antibiotics for prophylactic purposes and preservative-free artificial tears)

	

▪ Any systemic NSAID or opioids drugs (except occasional use of OTC formulations titrated no more than one single dose per week)

Relative day	
The relative day of an event that occurs prior to administration of IMP:
 

• Relative day = (Start date)-(Date of administration of IMP).

 
The relative day of an event that occurs on the same day or after administration of IMP:
 

• Relative day = (Start date)-(Date of administration of IMP)+1.

 
Consequently, Day 1 is the same day as the day of administration of IMP, Day -1 is the day before, and Day 2 is the day after.

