## 4. OVERALL DESIGN AND PLAN OF THE STUDY

### 4.1 Overview

This is a phase 3, randomized, parallel-group, double-masked, placebo-controlled, multicenter study.

This study will compare the efficacy and safety of clobetasol propionate ophthalmic nanoemulsion 0.05% to placebo (vehicle), when administering one drop QID during 14 days after routine unilateral cataract surgery.

Approximately a 15% of screening failures is expected. Overall, 210 patients are planned to be randomized into the study. They will be screened across 20 centers in the US. Patients who experience postoperative inflammation on the first day following routine cataract surgery and who meet all other eligibility criteria will be randomized to one of two study groups in a 2:1 ratio to receive either clobetasol propionate ophthalmic nanoemulsion 0.05% (N=140) or placebo (N=70) for the treatment of inflammation and pain associated with cataract surgery.

Patients will undergo routine cataract surgery according to the investigator's normal procedures.

The day of the cataract surgery will be considered Day -1 of the study, whereas the day of the randomization and the first administration of the IMP will be considered Day 1 of the study.

Six study visits are planned: Visit -1 (Screening; Day  $-7 \pm 3$  days), Visit 1 (Baseline; Day 1, 24h after the surgery), Visit 2 (Day 3 + 1 day), Visit 3 (Day 8  $\pm 1$  day), Visit 4 (Day 15  $\pm 2$  days), and Visit 5 (Day 29  $\pm 2$  days) (Table 1). An attempt should be made to schedule patients at approximately the same time during the day at each study visit.

If a patient wants to discontinue from the study, he/she will be treated according to the clinical practice. Patients who discontinue the study treatment will be requested to continue attending their remaining study visits. If the patient does not accept and wants to discontinue from the study, they will be encouraged to at least attend the Early Termination Visit (Section 4.3.2.8) as soon as possible.

An informed consent form (ICF) must be obtained from each patient prior to the commencement of any study procedure. All patients must be given ample time to review the ICF and to ask any question related to the study prior to their participation. All participant patients will be provided with a copy of the signed ICF.

[figure not shown]

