### 8.3.2 *Timing*

Adverse events will be recorded from the time of informed consent completion, throughout the study, and at early termination. Adverse events that were on-going when the patient completed the study will continue to be followed until resolution or until the investigator decides that the AE is stable; AEs will be coded using the MedDRA dictionary.

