### **8.3.3 Recording Adverse Events**

Volunteered, observed, and elicited AEs will be recorded. This includes AEs the patient reports spontaneously, those the investigator observes, and those elicited in response to questions from the study staff. Patients will be asked open-ended questions, such as "How have you been feeling since your last visit?", at each study visit.

All AEs that occur during the study must be recorded in the AE section of the eCRF. All AEs eCRF entries should contain a brief description of the event, date and time of onset, duration, intensity, treatment required, relationship to study medication, action taken with regard to study medication, outcome, and whether the event is classified as serious.

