#### **8.3.4.1 Severity**

Severity describes the intensity of an event. The severity of each AE must be assessed by the investigator and recorded on the eCRF as mild, moderate or severe according to the following definitions:

**Mild:** The AE does not interfere in a significant manner with the patient's normal functioning level. It may be an annoyance.

**Moderate:** The AE produces some impairment of function or it interferes with usual activities but not hazardous to health. It is uncomfortable and/or an embarrassment.

**Severe:** The AE produces significant impairment of functioning or incapacitation and/or it is a hazard to the patient. An AE that is assessed as severe should not be confused with a SAE. Severe is a category utilized for rating the intensity of an event; and both AEs and SAEs can be assessed as severe.

If an AE changes in severity, the worst severity should be reported.

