### 6.3.10 Adverse Events

AEs data are collected on the 'Adverse Events' eCRF form.

AEs will be coded according to the Medical Dictionary for Regulatory Activities (MedDRA) system, the latest version and tabulated by System Organ Class (SOC) and by Preferred Term (PT).

A Treatment-Emergent Adverse Event (TEAE) is defined as an AE observed after starting administration of IMP or placebo (see Section 6.3.1).

TEAEs will be summarized by presenting, for each treatment regimen, the number of events and the number and percentage of patients with:

- Any TEAE
- Any Serious Treatment Emergent Adverse Event (STEAE)
- Any TEAE of Special Interest (TEAESI)
- Any TEAE related to IMP/Placebo
- Any TEAE leading to treatment discontinuation (drug withdrawn)
- Any STEAE related to IMP/Placebo
- Any TEAESI related to IMP/Placebo

The number and percentage of TEAEs by causality and the number and percentage of mild moderate and severe TEAEs will be tabulated by SOC, PT and treatment arm. All tables with TEAEs by SOC and PT stratified by treatment regimen will only be counted by patient once within each PT.

The following tables will be provided with TEAEs by SOC and PT stratified by treatment regimen: TEAEs, TEAEs related to IMP/Placebo, TEAEs leading to discontinuation, STEAEs, STEAEs related to IMP/Placebo, TEAESI and TEAESIs related to IMP/Placebo.

TEAEs, STEAEs and TEAESIs will be tabulated by severity (mild, moderate or severe) and relationship to treatment (No: not related, unlikely related, Yes: possible, probable and certain). If a patient has more than one event with the same PT, the AE will only be counted once and the worst/maximal severity and the worst/strongest relationship will be used.

A listing of all AEs will be presented, whether treatment emergent or not. TEAEs will be flagged in this listing. A separate listing for deaths, STEAEs, AESIs and TEAEs leading to discontinuation will be provided (if any).

The following AEs (SOC, PT) of special interest (AESI) will be evaluated by Investigators at all study visits and time points (as applicable):

- IOP rise over 30 mmHg (SOC- INVESTIGATIONS, PT-INTRAOCULAR PRESSURE INCREASED)
- Pain/discomfort associated with IMP instillation (SOC-EYE DISORDERS, PT-EYE PAIN, OCULAR DISCOMFORT and related with IMP)

SAF will be used for all AE related summaries.

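### The TEAE formula in SAP 6.3.1 omits the worsening that its own definition includes, so an AE that keeps a pre-dose start date is missing from the TEAE tables even if it worsens on study drug

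*SAP*

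**What the plan says.** SAP 6.3.1 defines a treatment-emergent adverse event (TEAE) twice in one table cell. In words, it is an event that emerges during treatment, "having been absent pre-treatment or worsens relative to the pre-treatment state". As a rule, it is "First dose IMP/Pacebo date ≤ start date AE ≤ last dose IMP/Placebo date". SAP 6.3.10 adds a third description, "an AE observed after starting administration of IMP or placebo", and refers back to 6.3.1.

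The protocol sets what is recorded and when:

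- 8.3.2: "Adverse events will be recorded from the time of informed consent completion, throughout the study, and at early termination".
- 4.1: "The day of the cataract surgery will be considered Day -1 of the study"; the first dose is on Day 1.
- 8.3.4.1: "If an AE changes in severity, the worst severity should be reported".
- 8.3.3: "All AEs eCRF entries should contain a brief description of the event, date and time of onset, duration, intensity". Section 8.3.7 asks for a start time only where relevant.
- 8.3.1.1: a disorder already present at the first dose is an AE only if it gets significantly worse afterwards; baseline conditions belong in medical history. Section 7.5.2 has the Visit 1 history cover the time since screening.

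In the SAP output list, all AE tables (14.3.1.1 to 14.3.1.10) are confined to TEAEs. All AEs are listed, with TEAEs flagged (SAP 6.3.10, listing 16.2.7.1). Protocol 9.1.13 plans a tabulation of all AEs by SOC and PT, but the SAP table list has none.

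**The concern.** A programmer will code the inequality, not the sentence above it, and the inequality cannot detect worsening. This matters here because surgery falls between the start of AE collection and the first dose. Events that begin before dosing and are aggravated later are therefore a foreseeable class. Protocol 2.3 names raised IOP and impaired wound healing among the ocular risks of corticosteroids, and protocol 5.3 treats considerable worsening of an AE as a possible reason to stop study medication.

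SAP 6.3.10 compares safety descriptively only, so the counts by arm are the AE comparison. An event that drops out of them loses its place in the summaries of relatedness, seriousness and discontinuation.

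**Working it through.** No sample size, power or alpha figure is involved. The check sets the three SAP wordings side by side and applies them to boundary cases.

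**Step 1: the window.** Screening is Day -7 ± 3 days, that is Day -10 to Day -4. AE collection before the first-dose date therefore runs from there to Day -1, which is 4 to 10 calendar days including the day of surgery.

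**Step 2: boundary cases.** For illustration, the first dose is placed at about 10:00 on Day 1. The 6.3.10 wording is read as requiring onset after the first dose.

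| Case | 6.3.1 formula | 6.3.1 words | 6.3.10 wording |
|---|---|---|---|
| Onset Day -1 after surgery, no worsening | no | no | no |
| Onset Day -1 after surgery, worsens Day 4 | **no** | **yes** | no |
| Onset between consent and surgery, worsens Day 4 | **no** | **yes** | no |
| Onset Day 1 before first dose, no worsening | **yes** | **no** | no |
| Onset Day 1 before first dose, worsens Day 4 | yes | yes | no |
| Onset Day 1 after first dose | yes | yes | yes |
| Worsening entered as a new AE starting Day 4 | yes | yes | yes |

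Formula and words disagree in three of the seven cases. Two lose a worsening event. One adds an event that was present before any drug.

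**Step 3: which start date is entered.** The second and third rows apply only if the original date is kept. There are two routes through the protocol.

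- *Recorded as an AE at onset* (8.3.2 and the AE assessment at Visit -1). The record has a pre-dose start date. When the event worsens, 8.3.4.1 has the worst severity reported and mentions no new record or new date. The event fails the formula.
- *Recorded as medical history* (8.3.1.1 and 7.5.2). The disorder becomes an AE on significant worsening. If the date of worsening is entered as the start date, the event passes the formula. If the original onset is entered, it fails.

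Neither section fixes the date, so sites could differ.

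**Step 4: can the worded definition be programmed?** Neither the AE items in 8.3.3 nor those in 8.3.7 include a date of change in severity. A single record holding only the worst severity does not show whether that severity was reached before or after the first dose. A worsening clause in the SAP therefore needs a recording instruction with it.

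**Step 5: Day 1.** At Visit 1 the slit lamp, IOP, visual acuity and ophthalmoscopy examinations come before dosing on the same date (protocol 4.3.2.2). The formula compares whole dates and admits equality, so an AE with a Day 1 start is counted whether it began before or after the dose.

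**The case against.** The strongest reply is that the protocol already limits the problem. Under 8.3.1.1 and 7.5.2 a pre-dose disorder is medical history until it worsens, so the AE may well carry the date of worsening and be counted. Section 8.3.4.1 concerns the severity grade and does not forbid a new record. Both points stand, and they make the omission conditional. They do not remove it, because 8.3.2 and the Visit -1 AE assessment point the other way.

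The pool of events is also narrowed. Expected inflammation and pain after surgery are not AEs. Corneal abrasion or ulceration, intraoperative complications that may increase inflammation, and IOP ≥24 mmHg in the study eye at Visit 1 are exclusions. This stands, and the number affected may be small.

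A reader might infer that worsening under the steroid gets no count by arm at all. The documents do not support that. Table 14.3.4.2 gives IOP change from the Visit 1 baseline by arm, and table 14.2.11.7 compares change in corneal edema severity. These do not depend on AE start dates. They are a partial substitute: they carry no causality, seriousness or discontinuation, and SAP section 5 restricts efficacy visits to those on study drug without rescue or prohibited medication. The all-AE listing 16.2.7.1 also keeps the events, and the title of listing 14.3.2 is not confined to TEAEs, but a listing is not a comparison.

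On Day 1, counting same-date events is an inclusive convention applied alike in both arms, and the Visit 1 AE assessment is listed after dosing. That makes this part minor.

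**Conclusion.** The concern holds in conditional form. It is certain that the formula in SAP 6.3.1 contradicts the definition in the same cell and that 6.3.10 adds a third wording. It is conditional that events are lost: an AE with onset between consent and Day -1 is absent from tables 14.3.1.1 to 14.3.1.10 if its original start date is kept. This includes one that becomes serious (14.3.1.7) or leads to discontinuation (14.3.1.6).

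It would go too far to conclude that every pre-dose AE that worsens is lost, because the documents leave the start date open. The number of affected events is not given and cannot be derived. Counting pre-dose Day 1 events is a lesser defect, since it over-counts in both arms. No efficacy conclusion changes. The upper limit of the formula, the last-dose date, is a separate question not examined here.

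**What to change.** - **SAP 6.3.1.** Extend the formula so that an AE is also treatment-emergent if its onset is before the first dose and its severity or seriousness increases after the first dose. Align 6.3.10 with that text.
- **Recording.** Reconcile protocol 8.3.1.1 and 8.3.4.1 with one instruction, in the protocol or the eCRF guidelines: an AE ongoing at the first dose that later worsens gets a new record dated at the worsening. This makes the added clause computable and removes differences between sites.
- **Day 1.** Use onset time where it is recorded. If the time is missing, treat the event as a TEAE. Because 8.3.7 asks for time only where relevant, some Day 1 events will stay under the current convention.

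The cost is a few extra AE records, one wording change in the protocol or eCRF guidelines, and a short SAP edit. SAP 6.3.10 counts a patient once within each preferred term, so the extra records do not inflate patient counts by preferred term.

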### 6.2 Administration

Study medication will be supplied in single-dose vials containing 0.20 mL (approximately 0.17 mL deliverable volume) per vial. A medication kit contains 6 pouches with 2 strips of 5 vials in each pouch, for a total of 60 vials and a plastic bag labelled with the kit number.

The first dose of the IMP should be administered by the investigator or a designated study team member at Visit 1. After that, the investigator or a designated study team member will remove 4 vials from the opened pouch. He or she will place the removed vials (used one and unused ones) in a bag provided with the kit and store them at the study site in a secure location for traceability. The remaining 5 vials will be returned to the medication kit, for dispensation to the patient. Finally, the patient will receive a kit with 55 vials for their self-administration in the study eye QID for 14 consecutive days.

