#### **7.4 Secondary Safety Endpoints**

The secondary safety endpoints will be:

- Number, frequency and severity of AEs up to Day 29
- Number, frequency and severity of Serious AE (SAE) up to Day 29
- Proportion of patients discontinuing the study due to AEs
- Proportion of patients discontinuing the study due to lack of efficacy
- Change from Baseline to Day 3, Day 8, Day 15 and Day 29 compared to placebo in IOP
- Change from Baseline to Day 3, Day 8, Day 15 and Day 29 compared to placebo in physical and eye examination parameters and vital signs
- Use of concomitant medications up to Day 29

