### **8.3.5 Reporting Serious Adverse Events**

The investigator is responsible for ensuring that all SAEs occurring from the time of signing of ICF until 30 days following the final dose of the study drug must be reported to the Sponsor through [REDACTED] immediately, but in any event no later than 24 hours of any center personnel becoming aware of the event. Initial reports should be followed as soon as possible by detailed written reports. The initial and follow-up reports should identify patients by unique code numbers assigned in the study. The patients' names, personal identification numbers, and/or addresses must not be included neither in the attached documentation (when appropriate) and will never be provided to the Sponsor. The following information is **mandatory** for the initial report:

- Patient study ID
- Study treatment (masked, if applicable)
- Start date (time, if relevant) of the study treatment
- Brief description of the event (diagnosis)
- Start date (time, if relevant) of the event
- Seriousness criteria
- Causality assessment

For reported deaths, the investigator should supply the Sponsor with any additional requested information (e.g. autopsy reports and terminal medical reports).

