#### **9.1.13 Safety Analyses**

The total number of patients with at least one AE and the total number of AEs will be presented. The number of patients and the number of AEs overall and in each by randomized treatment group will be tabulated by SOC and by PT. AEs will also be tabulated versus worst severity and worst relationship to treatment. In this table, patients with AEs will be identified by their patient number.

The number of patients with TEAEs and the number of TEAEs overall and in each sub-set will be tabulated by SOC and PT. Frequency tables for the overall population and by each sub-set will also be presented for TEAEs related to study drug, TEAEs leading to study drug discontinuation, TEAEs of special interest, serious TEAEs (STAEs), and STAEs related to study medication. Additional summary tables will be provided for TEAEs with worst severity by SOC and PT per patient and TEAEs with worst relationship by SOC and PT per patient.

Listings of patients with STAEs, deaths and STAEs leading to discontinuation and individual narrative summaries for these cases will be provided. In the listings, patients with TEAEs will be identified by their patient number.

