### 3.3 Secondary Safety Endpoints

- Number, frequency and severity of adverse events (AEs) up to Day 29.
- Number, frequency and severity of serious AEs (SAEs) up to Day 29.
- Proportion of patients discontinuing the study due to AEs.
- Proportion of patients discontinuing the study due to lack of efficacy.
- Change from Baseline to Day 3, Day 8, Day 15 and Day 29 compared to placebo in intraocular pressure (IOP).
- Change from Baseline to Day 3, Day 8, Day 15 and Day 29 compared to placebo in physical and eye examination parameters and vital signs.
- Use of concomitant medications up to Day 29

The IOP will be assessed in both eyes using the Goldmann applanation tonometry method (for details see Appendix 3 of CSP).

[figure not shown]

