### 14.3 SAFETY DATA

#### Adverse events

Table	Title	Pop	Top.Line
14.3.1.1	Summary of Treatment Emergent Adverse Events (TEAEs)	SAF	X
14.3.1.2	Treatment Emergent Adverse Events by System Organ Class and Preferred Term	SAF	

14.3.1.3	TEAEs by SOC and PT by worst severity	SAF	
14.3.1.4	TEAEs by SOC and PT by worst relationship	SAF	
14.3.1.5	TEAEs related to IMP/Placebo	SAF	
14.3.1.6	TEAEs leading to discontinuation	SAF	
14.3.1.7	Serious TEAEs	SAF	
14.3.1.8	Serious TEAEs related to IMP/Placebo	SAF	
14.3.1.9	TEAEs AESI	SAF	
14.3.1.10	TEAEs AESI related to IMP/Placebo	SAF	
14.3.2	Listings of Deaths Other Serious Adverse Events, and Other Significant Adverse Events	SAF	

14.3.3 [This title is reserved for narratives.]

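### All adverse-event tables stop at the last dose, so about half of the Day 29 safety endpoint window gets no count by arm

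*SAP*

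**What the plan says.** - **Endpoint.** SAP 3.3 lists "Number, frequency and severity of adverse events (AEs) up to Day 29", with a matching item for serious events. Protocol 7.4 has the same pair, including "Number, frequency and severity of Serious AE (SAE) up to Day 29".
- **Treatment-emergent rule.** SAP 6.3.1 gives the date rule "First dose IMP/Pacebo date ≤ start date AE ≤ last dose IMP/Placebo date". SAP 6.3.10 words it more loosely but sends the reader back to that rule: "A Treatment-Emergent Adverse Event (TEAE) is defined as an AE observed after starting administration of IMP or placebo (see Section 6.3.1".
- **Outputs.** The AE tables in SAP 8.1 begin with 14.3.1.1, "Summary of Treatment Emergent Adverse Events (TEAEs", and run to 14.3.1.10. All ten are limited to treatment-emergent events, including the serious-event tables (14.3.1.7, 14.3.1.8) and the tables of events of special interest (14.3.1.9, 14.3.1.10). Other AEs appear only in Listing 16.2.7.1 and, where they qualify, in the listings under item 14.3.2.
- **Protocol analysis.** Protocol 9.1.13 plans tables of all AEs: "The number of patients and the number of AEs overall and in each by randomized treatment group will be tabulated by SOC" (and by preferred term). It then describes the treatment-emergent tables separately.
- **Collection.** AEs are assessed through Visit 5 (Day 29 ± 2). For serious events, Protocol 8.3.5 says "all SAEs occurring from the time of signing of ICF until 30 days following the final dose of the study drug must be reported".
- **Dosing.** After one dose at the clinic, "the patient will receive a kit with 55 vials for their self-administration in the study eye QID for 14 consecutive days" (Protocol 6.2). SAP 6.3.8 sets the planned doses at 56.

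**The concern.** The endpoint and the tables meant to report it cover different periods. Treatment lasts 14 days and follow-up runs to Day 29, but the date rule closes on the day of the last dose. SAP 6.3.10 says the arms are compared on safety descriptively, with no inferential comparison. The AE tables are therefore the main by-arm comparison of AEs, and a listing does not give number and frequency by arm.

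Three consequences follow.

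1. The SAP drops an analysis that the protocol plans and does not say so.
2. Raised intraocular pressure (above 30 mmHg) is an event of special interest, to be evaluated at all visits. A rise first found and dated at Visit 4 on Day 15, in a patient whose last dose was on Day 14, is not treatment-emergent. The same holds for any rise first found at Visit 5. Neither enters Tables 14.3.1.9 and 14.3.1.10. Measured pressure to Day 29 is still summarised by arm in Table 14.3.4.2, so for pressure only the event counts are affected.
3. The window closes early for anyone who stops study medication. Under Protocol 6.7.2 a rescued patient stops study medication while visits continue as far as possible. If stopping rates differ between arms, AEs are counted over different lengths of time. The documents give no such rates, so this is a risk and not a demonstrated bias.

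**Working it through.** **Inputs.** One clinic dose plus 55 dispensed vials, four times daily for 14 days (Protocol 6.2); 56 planned doses (SAP 6.3.8); endpoint to Day 29 (Protocol 7.4, SAP 3.3); Visit 5 on Day 29 ± 2 (Protocol 4.3.2.6); serious events collected to 30 days after the final dose (Protocol 8.3.5).

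**Reproducing the plan's figure.** 1 + 55 = 56 and 4 × 14 = 56, matching the SAP.

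**Day of the last dose.** With four doses on Day 1, 56 − 4 = 52 = 13 × 4 remain, so the last dose is on Day 14. With one to three doses on Day 1, 52 doses on Days 2 to 14 leave three to one for Day 15.

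**Share of time outside the window** = (end day − last-dose day) / end day:

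| End of follow-up | Last dose | Days outside | Share |
|---|---|---|---|
| Day 29 | Day 14 | 15 | 15/29 = 51.7% |
| Day 29 | Day 15 | 14 | 14/29 = 48.3% |
| Day 27 (earliest Visit 5) | Day 15 | 12 | 12/27 = 44.4% |
| Day 31 (latest Visit 5) | Day 14 | 17 | 17/31 = 54.8% |

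**Early stopping** (stop days chosen as illustrations). Last dose on Day 8: 21/29 = 72.4% outside. Last dose on Day 3: 26/29 = 89.7% outside.

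**Serious events against their collection period from first dose.** 14 + 30 = 44 days, 30/44 = 68.2% outside; 15 + 30 = 45 days, 30/45 = 66.7% outside. The serious-event tables thus cover about the first third of that period.

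**Unequal windows between arms** (rescue rates and rescue on Day 4 are assumptions; other patients complete on Day 14). Mean counted window = (1 − r) × 14 + r × 4.

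| Rescued, active / placebo | Mean days, active | Mean days, placebo |
|---|---|---|
| 5% / 10% | 13.5 | 13.0 |
| 5% / 30% | 0.95 × 14 + 0.05 × 4 = 13.5 | 0.70 × 14 + 0.30 × 4 = 11.0 |
| 10% / 40% | 13.0 | 10.0 |

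**The case against.** The best defence is that the definition is not itself an error. The SAP cites ICH E9 for events that emerge during treatment, and a window ending at the last dose is a fair reading of that. It also has a purpose: rescue can include corticosteroids, and a window to Day 29 would attribute events after rescue to the randomised arm, placebo included. On this view the defect is narrower: the protocol's all-AE tables are missing, and adding them would meet the endpoint with SAP 6.3.1 unchanged. Further, nothing is lost, since the listings hold every event and counts for 210 patients could be rebuilt.

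Much of this stands as qualification. An on-treatment view is legitimate and should be kept. Restoring the all-AE tables is a sufficient minimum repair. The effect also differs by table. Pain or discomfort on instillation, the other event of special interest, can hardly arise anew once instillation has ended. Events leading to drug withdrawal (Table 14.3.1.6) nearly always start by the last dose. The figure of 67% to 68% for serious events is measured against the collection period; against the Day 29 endpoint the share is the same 48% to 52% as for other AEs.

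None of this supplies by-arm counts after the last dose. The looser wording in SAP 6.3.10 does not either, because it defers to 6.3.1. That counts could be rebuilt later is a reason to plan them now, before unmasking.

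**Conclusion.** The concern holds. For a patient who completes treatment, 48% to 52% of the endpoint window to Day 29 has no AE or serious-AE count by arm (44% to 55% across the Visit 5 window), and more for a patient who stops early. This assumes dosing as scheduled and the date rule in SAP 6.3.1 applied as written. All figures are shares of time; the share of events that would go uncounted cannot be estimated from the documents. It should be corrected before unmasking, because the SAP as written does not report a stated safety endpoint, serious events included, and departs from Protocol 9.1.13 without saying so.

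**What to change.** **Preferred.** Define treatment-emergent as onset or worsening from the first dose through Visit 5 (Day 29) or study exit. State the same window in SAP 6.3.1 and 6.3.10, and build Tables 14.3.1.1 to 14.3.1.10 on it. Split the counts by arm into on-treatment and post-treatment, and mark events that start after rescue medication.

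**Minimum.** Leave the definition alone and add the all-AE tables by arm to Day 29 that Protocol 9.1.13 plans.

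**In either case.** State how serious events that start after Visit 5 but within 30 days of the final dose will be presented.

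**Minor, same section of code.** SAP 6.6 imputes day 15 when only month and year are known. For a patient first dosed on the 16th or later, an AE start in that same month would be placed before the first dose. Use the first-dose date when month and year match it.

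**Cost.** A change of definition in the SAP and re-programming of a few tables, with no new data. AE percentages may rise slightly and will include events after rescue, which is why the on-treatment and post-treatment split is needed.
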